The Phase 3 study was a 12-week, double-blind, randomized, placebo-controlled, parallel group study evaluating the safety and efficacy of solriamfetol for the treatment of excessive sleepiness and impaired wakefulness in patients with narcolepsy. Patients were randomized 1:1:1:1 to receive daily placebo or solriamfetol 75 mg, 150 mg, or 300 mg, and randomization was stratified by the presence or absence of cataplexy. The co-primary study endpoints were the change from baseline to Week 12 in mean sleep latency on the MWT and the change from baseline to Week 12 in the ESS score. The key secondary endpoint was the percentage of patients who reported improvement on the Patient Global Impression of Change (PGI-C) at week 12. Evaluation of safety included adverse events (AEs), laboratory tests, and vital signs.

Of the 239 patients randomized, 236 received at least one dose of study drug and were included in the safety population.² The modified intention to treat (mITT) population consisted of 231 patients, of whom 58 patients were randomized to placebo, 59 patients to solriamfetol 75 mg, 55 patients to solriamfetol 150 mg, and 59 patients to solriamfetol 300 mg. A total of 195 patients completed the study (52 patients in the placebo group, 49 in the solriamfetol 75 mg group, 51 in the solriamfetol 150 mg group, and 43 in the solriamfetol 300 mg group). In the mITT population (n=231), the discontinuation rate was highest in the solriamfetol 300 mg group (27.1%) compared with the placebo (10.3%), solriamfetol 75 mg (16.9%), and solriamfetol 150 mg (7.3%) groups. The most common reasons for discontinuation in the solriamfetol 300 mg group were lack of efficacy (10.2%, n=6) and adverse events (8.5%, n=5).

Open Label Safety Study of Solriamfetol to Promote Wakefulness and Improve Cognition and Quality of Life in
 Patients with Primary Gliomas
 Wake Forest Baptist Comprehensive Cancer Center
 WFBCCC 98418

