Secondary hypotheses include that solriamfetol treatment at maximal patient specific dosing will result in improvements in patient-reported excessive daytime sleepiness and sleep quality (e.g. ESS and PSQI), neurocognitive function (see below for neurocognitive battery), fatigue and mood (e.g. Brief Fatigue Inventory, Cancer Fatigue Scale, Beck Depression Inventory), and quality of life (FACT-Brain).

3. Exploratory Hypotheses

Improvements in objective measures of sleep (e.g. actigraphy, sleep diary) will be similar to those reported in prior studies (e.g. obstructive sleep apnea, narcolepsy). We hypothesize that improvements in sleep, neurocognition, fatigue, mood, and quality of life may vary by clinical factors such as corticosteroid use, antiepileptic use, and tumor grade by World Health Organization (WHO) classification.

3 Objectives

1. Primary Objective(s)

1. To estimate the safety of solriamfetol at 75 mg daily, 150 mg daily, 300 mg daily as assessed by NCI CTC Adverse Events (v5.0) in patients with primary gliomas compared to prior studies⁴⁵⁻⁴⁷

2. Secondary Objective(s)

1. To estimate the effect of solriamfetol on sleep by Epworth Sleepiness Scores (ESS) scores in patients with primary gliomas and compare the effect to previously published scores in patients with OSA
2. To estimate the effect of solriamfetol on sleep quality by Pittsburgh Sleep Quality Index scores
3. To estimate the effect of solriamfetol on neurocognitive function based on a disease-specific neurocognitive battery (see neurocognitive battery below)
4. To estimate the effect of solriamfetol on patient-reported fatigue (Brief Fatigue Inventory, Cancer Fatigue Scale) & mood (Beck's Depression Inventory)
5. To estimate the effect of solriamfetol on patient-reported QOL (FACT-Br)
6. To estimate the effect of solriamfetol on objective sleep-wake times by actigraphy and sleep diary (pre- vs post-treatment)

3. Exploratory Objective(s)

1. To explore a biologic gradient effect of increasing doses of solriamfetol on actigraphy
2. To explore differences in clinical activity of solriamfetol by corticosteroid use, antiepileptic use, and tumor grade

4 Patient Selection

Inclusion and exclusion criteria represent standard criteria for other sleep studies in this population (e.g. inclusion criteria) and standard exclusions for prior studies of this agent (e.g. exclusion criteria).^{8,39,40}

1. Inclusion Criteria

1. WHO Grade 2-4 infiltrating glioma by histologic confirmation

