This is a single-arm, open label, two-part safety study of solriamfetol in patients with WHO grade 2-4 gliomas. Patients with stable disease by clinical examination and neuroimaging who have an ESS \geq 10 and meet all inclusion/exclusion criteria will be recruited and enrolled. First, all patients will receive solriamfetol at escalating doses. Second, all patients will complete a fixed dose drug continuation treatment at the patient-specific maximum tolerated dose.

The study will occur in 3 phases:

Open Label Safety Study of Solriamfetol to Promote Wakefulness and Improve Cognition and Quality of Life in
Patients with Primary Gliomas
Wake Forest Baptist Comprehensive Cancer Center
WFBCCC 98418

1. Pre-Treatment Baseline (~1 week)
2. Flexible Dose Titration (~3 weeks)
3. Fixed Dose Drug Continuation (~6 weeks)

Patients will initially complete a 1-week baseline actigraphy and sleep diary prior to treatment initiation to establish a baseline sleep pattern.

Solriamfetol will be dosed by flexible dose titration starting at 75 mg daily in all patients and escalating after 7 days (1 week) to 150 mg daily and then after 7 days to 300 mg daily for a total duration of 3 weeks (flexible dose titration period). Patients who experience a dose-limiting toxicity will be de-escalated to the last tolerated dose level and move to the fixed dose drug continuation phase. Prior studies incorporating this design have used a 3-day treatment prior to escalation.⁴⁹ For this study, 7 days has been selected to provide a sufficient period of time to observe both immediate and delayed toxicities that could be seen in this population.

Following completion of the flexible dose titration, patients will continue solriamfetol at 300 mg daily or their maximally tolerated dose for a treatment duration of 6 weeks. For this period of the study, 8 weeks has been selected to allow for time to observe both short term improvement in patient-reported sleep as well as potentially more delayed changes in other study endpoints (i.e. fatigue, mood, neurocognition).

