Pittsburgh Sleep Quality Index (PSQI)		X				X	X	
Associated Symptom PROMs: BFI, CFS, BDI		X				X	X	
QOL PROMs: FACT-Br		X				X	X	
Neuro-cognitive Battery		X					X	
Standard of Care MR Brain ^a	X						X ^j	

¹ Patient's undergoing telehealth assessment at the pre-screening timepoint require virtual examination by observation only. Blood draw and laboratory testing can be performed locally and reviewed remotely.

^a Pre-study requirements listed in table must be completed **within** 21 days prior to registration.

^b Blood pressure (mmHg), heart rate (BPM)

^c Height, Weight, M² Patients undergoing telehealth assessment can provide this information verbally using home device (e.g. scale).

^d Albumin, alkaline phosphatase, total bilirubin, bicarbonate, BUN, calcium, chloride, creatinine, glucose, potassium, total protein, SGOT[AST], SGPT[ALT], sodium.

^e Serum pregnancy test (women of childbearing potential).

^f May be performed by telephone.

^g Epworth Sleepiness Scale (ESS) will be completed either in the clinic (D1, D29, D70) at each of the study visits (V1, V2, V3) or by telephone (D8, D15, D22) during the flexible dose escalation portion of the study.

^h 7-day sleep diary is to be completed at baseline (D1-7), continuously during dose escalation (D8-14, D15-21, D22-28), and during the first and last week of fixed dose drug continuation (~D29-35 and ~D63-70). Actigraphy will be collected continuously.

ⁱ Patients may complete the baseline sleep diary and actigraphy prior to the Baseline Visit (V1) or after the Baseline Visit (V1).

^j Post-treatment MR Brain is to be performed D85 \pm 42 days.

^k Study visits may be conducted via telehealth visit. Blood draw and EKG (when appropriate) can be performed locally and reviewed remotely.

3. Screening

Glioma patients seen at the Wake Forest Baptist Medical Center will be considered for eligibility at or before their scheduled visits. In general, patients may be approached at the time of routine outpatient visit for follow up with neuro-oncology, medical oncology, radiation oncology, and neurosurgery.

Patients who are identified as potential study candidates will have an opportunity to hear about the study and complete written informed consent. Patients who sign informed consent and do not meet eligibility criteria will be considered screen failures, will not be evaluable for the primary endpoint, will not count toward the total sample size, and this enrollment will be replaced.

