ESS score is the most important secondary outcome in this study. We also calculate the power to test whether the pre-post change is different from 0 and test whether the change is different from the pre-post change in the prior studies which recorded the pre-post changes for patients at 75 mg, 150 mg, and 300 mg. At an alpha of 0.10, a two-sided test, and cohort sample size of 36 patients, the study will have 80% power to detect the mean difference of 1.01 point ($=0.42$ standard deviation (SD)) in ESS score from the study sample. The mean differences are reasonable. We should have enough power for our analysis.

Prior studies of solriamfetol in patients with narcolepsy have demonstrated improvement in ESS scores at Week 8 of -3.4 (75 mg daily), -5.2 (150 mg daily), -6.4 (300 mg daily), and -2.1 (placebo) with baseline ESS ranging from 16.9-17.3. In patients with OSA, Week 8 improvements were -6.3 (75 mg daily), -6.9 (150 mg daily), -7.7 (300 mg daily), and -3.8 (placebo) in patients with baseline ESS ranging from 14.8 to 15.6. In our prior study mean ESS score for patients with primary brain tumors who would be eligible for the proposed study (i.e. ESS \geq 10) was 14.8 (SD: 2.4). For the current study, we will use the data from the prior OSA study as a comparator given that baseline ESS scores were similar to what we anticipate in the to-be-enrolled cohort. Based on this, the study hypothesizes that treatment with solriamfetol at 75 mg, 150 mg, or 300 mg will achieve at least a 6.3 point difference (75 mg daily) and up to 7.7 point difference (300 mg daily) in ESS scores at Week 10 (baseline vs V3). This will be compared to a null difference of 3.8 (placebo arm in OSA study). This mean change in ESS scores is clinically meaningful as has been reported.⁵³ In order to detect the differences between the mean change ESS score from the proposed study to the mean change of 3.8 in the placebo arm in OSA study, the detectable mean change needs to be greater than 5.4 in the study sample in order to reach 80% power. We hypothesize that the mean change in this study sample ranges from 6.3 to 7.7, which is higher than 5.4. We should have sufficient power to detect the difference between the mean change ESS score in our study sample and that in the placebo arm in the OSA study.

5. Estimated Accrual Rate

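### 75 mg and 150 mg are each taken for only 7 days, but their safety is to be compared dose by dose with mostly 12-week trials without allowance for exposure time; separately, the V3 ESS hypothesis carries dose labels that V3 data cannot test

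*Combined protocol and SAP*

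**What the plan says.** **Dosing.** Section 7.1 starts everyone at 75 mg, "escalating after 7 days (1 week) to 150 mg daily and then after 7 days to 300 mg daily". Patients then take 300 mg, or their own maximum tolerated dose, for 6 weeks. A dose-limiting toxicity (DLT) at 150 mg sends the patient back to 75 mg, and one at 75 mg ends treatment (7.9.1).

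**Safety.** Objective 3.1 is "To estimate the safety of solriamfetol at 75 mg daily, 150 mg daily, 300 mg daily as assessed by NCI CTC Adverse Events (v5.0") and sets the results beside references 45-47, the phase 3, 2b and 2a narcolepsy trials. The primary hypothesis in 2.1 is also framed by dose. Section 13.1 tabulates AEs by dose and compares doses by chi-squared or Fisher's test. It mentions neither exposure time nor the dose to which a fixed-phase event belongs.

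**Comparators (1.5.1).** In phase 3, "Patients were randomized 1:1:1:1 to receive daily placebo or solriamfetol 75 mg, 150 mg, or 300 mg", for 12 weeks. Phase 2b gave 150 mg for 4 weeks and then 300 mg for 8. Phase 2a gave 150 mg for one week and 300 mg for the next, but its AEs are reported here only for the two doses combined.

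**ESS.** Section 13.4 states that solriamfetol "will achieve at least a 6.3 point difference (75 mg daily) and up to 7.7 point difference (300 mg daily") at Week 10, baseline against V3, compared with 3.8 for placebo. The figures are OSA Week 8 values. ESS is also collected "by telephone (D8, D15, D22) during the flexible dose escalation portion of the study" (7.2, footnote g) and at V2 on D29, but Section 13 does not use these readings.

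**The concern.** An AE proportion grows with time at risk. Seven days at 75 mg set beside 12 weeks at 75 mg can look as safe as the published experience, or safer, even if glioma patients tolerate the drug worse. Section 13.4 says the trial will give safety profiles for three doses and inform a later randomized study, so that misreading would carry forward.

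The ESS sentence raises a separate problem. It names a 75 mg and a 300 mg effect at a visit where dose is set by tolerance. No unselected group will have stayed on 75 mg until V3.

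**Working it through.** **1. Exposure.** From the 7.2 schedule: 75 mg on D8-14, 150 mg on D15-21, 300 mg on D22-28, final dose on D29-70. That is 7 + 7 + 7 + 42 = 63 days, or 9 weeks. A patient who tolerates 300 mg has 7 days at each lower dose and 49 days at 300 mg. (Section 7.1 mentions both 6 and 8 weeks for the fixed phase. I use 6, which fits D29-70.)

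**2. What a 7-day window shows.** Let p be the 12-week proportion. Section 13.4 uses 10% and 20%. Under constant hazard (an assumption), the proportion by week w is 1 - (1 - p)^(w/12).

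| p at 12 weeks | 1 week | 9 weeks | 1 week, if all events start in week 1 |
|---|---|---|---|
| 10% | 0.9% | 7.6% | 10% |
| 20% | 1.8% | 15.4% | 20% |

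The shortfall at 7 days lies between the constant-hazard figure and none. Over 9 weeks it is modest even under constant hazard.

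**3. Could a real excess be hidden?** Suppose the hazard in glioma is doubled and a share s of the cumulative hazard falls in week 1. The 7-day proportion is 1 - (1 - p)^(2s). For illustration take p = 21%, headache in narcolepsy for all doses combined (Section 10.1, Table 2):
- s = 1/12 (constant hazard): 1 - 0.79^(1/6) = 3.9%
- s = 0.5: 1 - 0.79^1 = 21%
- s = 0.7: 1 - 0.79^1.4 = 28%
- s = 1: 1 - 0.79^2 = 37.6%

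A doubling stays hidden if half or less of the hazard falls in week 1, and shows if more does. The documents do not give s. They do suggest front-loading: in the OSA withdrawal study (1.5.2) AEs occurred in 48.9% during a 2-week titration and 10.2% during the 2 stable weeks that followed, although dose increases contributed to the first figure.

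**4. Who is on 75 mg at V3?** Section 13.4 expects 36 at 75 mg, at least 33 at 150 mg and at least 30 at 300 mg. With 33 and 30, 33 - 30 = 3 would step back to 75 mg. Because both figures are minimums, all 36 might reach 150 mg and 30 reach 300 mg, which gives 6. These counts cover titration only. A further reduction from 150 mg in the fixed phase could add a few, also selected by toxicity.

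**5. ESS power.** The plan's own figure comes first. For N = 36 and two-sided alpha 0.10, 13.4 says that "the study will have 80% power to detect the mean difference of 1.01 point". With the baseline SD of 2.4, a one-sample t-test (noncentral t) gives 0.423 x 2.4 = 1.01 points, so it reproduces. The documents give no SD of change, so I range it from 2.4 to 6 (an assumption). Power for a true change of 6.3 against 3.8, two-sided alpha 0.10:

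| SD of change | n = 36 (pooled) | n = 6 | n = 3 |
|---|---|---|---|
| 2.4 | >99% | 71% | 34% |
| 3.4 | >99% | 47% | 23% |
| 4.5 | 95% | 32% | 18% |
| 6 | 79% | 23% | 14% |

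The pooled test holds up. The 75 mg subgroup is too small, and a larger one would still be selected by toxicity.

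**The case against.** **The ESS hypothesis is best read as pooled.** Section 13.4 restates it as a range for the study-sample mean, 13.2 plans one one-sample t-test, and 2.2 already words the secondary hypothesis at each patient's maximum dose. This stands, so the ESS defect is one of labelling. A reader might infer that a 7-day ESS at 75 mg is to be tested against Week 8, making 6.3 too large by 1.9 points (Table 4 gives 4.4 at Week 1). The plan makes no such test. V3 follows about 9 weeks on drug, where Week 8 is a fair match.

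**The comparators are not all 12-week fixed-dose trials.** Phase 2a stepped weekly, and phase 2b, the comparator cited in 7.1, stepped its dose. This also stands. However, neither gave 75 mg, and neither supplies a 7-day AE figure for 150 mg alone in these documents.

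**The AE power statement is for combined doses, and 13.4 calls the study mainly descriptive.** True, and no per-dose external test is specified in 13.1. Objective 3.1 and hypothesis 2.1 still invite the dose-by-dose reading.

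**The direction of bias is not certain.** Front-loading shrinks the shortfall. Escalating only those who tolerated the lower dose also flatters 300 mg. So it goes too far to state as fact that the lower doses will look safer than they are.

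A reader might also infer that nearly everyone is on 300 mg at V3. Section 13.4 estimates how many receive it, not how many stay on it. In the OSA withdrawal study 53.5% were on 300 mg in the stable phase.

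**Conclusion.** The concern holds in two limited parts.

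First, the dose-by-dose safety comparison is confounded with exposure time. A 7-day AE proportion at 75 or 150 mg probably understates risk relative to the cited trials. For 12-week rates of 10-20%, the 7-day figure lies between 0.9-1.8% (constant hazard) and 10-20% (all onset in week 1). The documents do not locate it within that range.

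Second, the dose labels on the V3 ESS hypothesis cannot be tested, because about 3 patients, up to 6 on the protocol's titration estimates, would be on 75 mg, each after a toxicity. The pooled test against 3.8 is sound: power is about 95% or more for an SD of change up to 4.5, and 79% at 6.

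The 7-day steps are reasoned in 7.1 and are not criticized here. The change should be made because these results are meant to inform a later trial.

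**What to change.** **3.1 and 13.1.** Limit the comparison with 12-week trials to AEs over the whole treatment period (about 9 weeks). Label 75 and 150 mg results as first-week tolerability. Report AE rates per patient-week at each dose beside the proportions, and assign fixed-phase events to the dose being taken. Both measures are needed. If a 20% incidence all arises in week 1, the 7-day rate is 20 per 100 patient-weeks against roughly 20/12 = 1.7 averaged over 12 weeks, so a rate alone would err in the other direction.

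**13.4.** State the V3 ESS hypothesis for the pooled sample at patient-specific maximum dose, as 2.2 does, without dose labels.

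**Optional, 13.2.** If ESS by dose-week is reported, call it descriptive. Only D15 (75 mg) matches the Week 1 OSA values in Table 4. D22 and D29 follow 2 and 3 weeks of cumulative drug and should be noted as such.

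**Cost.** Revised wording and a small table from data already collected. The sponsor gives up dose-specific claims at 75 and 150 mg beyond one week.

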Appendix A – Eligibility Checklist

IRB Protocol No.	WFBCCC Protocol No.
Study Title: Open Label Safety Study of Solriamfetol to Promote Wakefulness and Improve Cognition and Quality of Life in Patients with Primary Gliomas	
Principal Investigator: [name]	

Inclusion Criteria (as outlined in study protocol)	Criteria is met	Criteria is NOT met	Source Used to Confirm * (Please document dates and lab results)
1 WHO Grade 2-4 infiltrating glioma by histologic confirmation 
 Where appropriate results from clinically available testing of isocitrate dehydrogenase (IDH) gene mutation status (for all gliomas), chromosome 1p and 19q deletion status (for suspected oligodendroglomas), and MGMT gene promoter methylation status (for malignant gliomas) must be available in the patient's chart. These studies are standard of care molecular studies that are performed as a part of routine clinical practice and allow for integrated molecular subtyping of primary glial tumors. 			
2 Epworth Sleepiness Scale (ESS) score ≥ 10 within 21 days of enrollment			
3 Clinical and/or radiographic evidence of stable disease within 21 days of enrollment			
4 Patients must have completed concurrent chemoradiation with recovery of all pre-existing toxicity to CTCAE Grade >1 
 Patient who are anticipated to undergo surgery and/or radiation therapy for management of their tumor during the duration of study treatment are NOT eligible. Patients who are anticipated to undergo adjuvant chemotherapy are eligible as long as there is no evidence of tumor progression by clinical exam and/or imaging within 21 days of enrollment (see 4.1.2). This determination should be made by clinical documentation and if there is question discussed with the Study Chair. Adjuvant chemotherapy is not an exclusion. Patients who are currently undergoing chemotherapy, targeted therapy, immunotherapy, or salvage treatment and have stable disease by imaging are eligible and can continue the current anti-cancer therapy. Patients who will require a new anti-cancer treatment or are anticipated to change anti-cancer treatments are not eligible. 			
5 Age ≥ 18 years			
6 Karnofsky performance status $\geq 60\%$			
7 Life expectancy of greater than 4 months			
8 Patients must have normal organ and marrow function as defined below: 
 leukocytes $\geq 3,000/\text{mcL}$ absolute neutrophil count $\geq 1,500/\text{mcL}$ platelets $\geq 100,000/\text{mcL}$ total bilirubin 1.5 X institutional ULN AST(SGOT)/ALT(SGPT) ≤ 2.5 X institutional ULN creatinine within normal institutional limits OR $\geq 50 \text{ mL/min}/1.73 \text{ m}^2$ for $\text{Cre} > \text{ULN}$ creatinine clearance 			

Open Label Safety Study of Solriamfetol to Promote Wakefulness and Improve Cognition and Quality of Life in
 Patients with Primary Gliomas
 Wake Forest Baptist Comprehensive Cancer Center
 WFBCCC 98418

9	The effects of solriamfetol on the developing human fetus are unknown. For this reason women of child-bearing potential and men must agree to use adequate contraception (hormonal or barrier method of birth control; abstinence) prior to study entry and for the duration of study participation. Should a woman become pregnant or suspect she is pregnant while participating in this study, she should inform her treating physician immediately			
10	Ability to understand and the willingness to sign an IRB-approved informed consent document (either directly or via a legally authorized representative)			
Exclusion Criteria (as outlined in study protocol)		Criteria NOT present	Criteria is present	Source Used to Confirm * (Please document dates and lab results)
1	Receiving active radiation therapy (including patients who are within 28 days of completing radiation therapy)			
2	Anticipated to undergo radiation therapy or require neurosurgical intervention during the period of active treatment (i.e. within the next 4 months)			
3	Contraindication to solriamfetol based on drug-drug interactions or concurrent systemic illness that precludes drug treatment			
4	Patients who have not recovered to <CTCAE grade 2 toxicities related to prior or current therapy are ineligible. 
 • Exception for laboratory-based or other adverse event that is stable and not anticipated to interfere with study related treatment must be reviewed and approved by the Study Chair. 			
5	Customary bedtime later than midnight			
6	Known and/or documented history of obstructive sleep apnea (OSA)			
7	Uncontrolled behavioral or psychiatric disorder (including suicidal ideation)			
8	Current excessive caffeine use (>600 mg/day or >6 cups of coffee/day)			
9	Current or prior history of alcohol or drug abuse within the last 2 years as assessed by the treating clinician			
10	Nicotine dependence that is currently interfering with sleep based on assessment by the treating clinician			
11	Concurrent use of selective serotonin or norepinephrine reuptake inhibitors (e.g. SSRI, SNRI) within 14 days of study enrollment 
 • Patients who are currently taking these agents may be tapered at the direction of the treating physician prior to study enrollment. • Patients taking other medications such as narcotics, benzodiazepines, antipsychotics, antiepileptics, corticosteroids, or over-the-counter sleep aids can be enrolled. It is recommended that the doses of these medications remain the same throughout the portion of active study treatment unless there is a medical indication for dose adjustment which will be determined by the treating physician (see Section 7.10). 			
12	History of allergic reactions attributed to compounds of similar chemical or biologic composition to solriamfetol			

Open Label Safety Study of Solriamfetol to Promote Wakefulness and Improve Cognition and Quality of Life in
 Patients with Primary Gliomas
 Wake Forest Baptist Comprehensive Cancer Center
 WFBCCC 98418

13 Uncontrolled intercurrent illness including, but not limited to ongoing or active infection, symptomatic congestive heart failure, unstable angina pectoris, cardiac arrhythmia, or psychiatric illness/social situations that would limit compliance with study requirements			
14 Pregnant women are excluded from this study because there is an unknown but potential risk for adverse events in nursing infants secondary to treatment of the mother with –solriamfetol, breastfeeding should be discontinued if the mother is treated with solriamfetol			

This subject is eligible / ineligible for participation in this study.

OnCore Assigned PID: _____

Signature of research professional confirming eligibility: _____ Date: _____

Signature of Treating Physician: _____ Date: _____

Signature of Principal Investigator**: _____ Date: _____

* Examples of source documents include clinic note, pathology report, laboratory results, etc. When listing the source, specifically state which document in the medical record was used to assess eligibility. Also include the date on the document. Example: "Pathology report, 01/01/14" or "Clinic note, 01/01/14"

**Principal Investigator signature can be obtained following registration if needed

